3. Evaluate the prototype app by having 60 daily adult smokers recruited through social media to complete the first 3 modules. Usability data, system log data on program use, and participant satisfaction data will also be analyzed. Input from participants will be gathered to incorporate additional features to be developed during Phase II. Significant changes in quit attempts, number of days without smoking (smokefree days) and changes in smoking attitudes and behavior will be used to determine the efficacy of the Phase I program and evidence for proceeding to Phase II development and evaluation.

B. SIGNIFICANCE

B.1. Importance of smoking cessation

Smoking is the leading cause of preventable death in the U.S.,^{1,2} accounting for approximately 443,000 deaths, which is 20% of all deaths annually.^{1,23} Despite overall declines in the rate of tobacco use in the United States over the past 30 years, improving quit rates among current smokers continues to be a significant public health focus given the high risk for long-term negative health outcomes.² There has been extensive research evaluating a wide range of smoking cessation approaches over the past 40 years, and the 2008 Clinical Practice Guideline for treatment of tobacco use and dependence summarized the efficacy of smoking cessation approaches based on more than 8700 research articles. Although there has been significant progress in the application of both clinical and public health interventions aimed at smoking cessation, researchers have concluded that the overall success rate of these interventions has not shown significant improvement.³ New, innovative, theory-driven approaches are needed to both improve the overall abstinence and long-term quit rates, as well as to increase the reach of effective interventions.

B.2. Cognitive Dissonance-based intervention approaches

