We will present the initial prototype to five test users for preliminary usability testing in which the participant will be observed using the program and then asked to talk aloud about their experience to help us better understand ease of navigation and program use. Observations and interviews with usability participants is a great help in discovering potential problems with program navigation comprehension of key concepts and interactive activities. Mobile app-based components will embody established usability standards and will adhere to their recently emerging usability guidelines. Individual test sessions will be held, with hands-on use of functioning program components. Based on our observations and interviews we will move on to conduct a more complete programming of the proposed intervention and prepare for pilot testing. One unique feature of the CDI program will be the use of video for making public statements about attitudes, beliefs and intentions. The usability testing will allow us to fully test the use of the video feature with adult participants who currently smoke. The program will be used by the participants on their own mobile devices to emulate the way that the program will be used in the evaluation study. The key features that need testing will be the video components that are recorded and posted by participants. We will test the ability of participants to upload video to the app and our ability to view and upload the video to their support group. The platform will allow us to view and monitor the video before it is shared with the support group of peers.

D.4.2. Stage 2: Product Evaluation (N=60)

We will conduct a pilot test of the CDI mobile app with 30 male and 30 female adult smokers (N=60). Feasibility, usability, participant satisfaction, and pre-/post- intervention outcomes of smoking will be evaluated in the pilot study. Data on: 1) frequency and duration of app use, 2) number of modules completed, 3) cognitive dissonance and motivation to quit, and 4) smoking attitudes and behavior, including motivation to quit, quit attempts, and number of days without smoking (smokefree days), will be examined pre- and post-intervention. Participants will be compensated using gift cards to Amazon in the following increments: \$30 for the baseline assessment, \$35 for the 1-month assessment, and \$40 for the 3-month assessment.

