A full description of measures is included in the Human Subjects. Briefly, the following will be used to examine pre- and post- changes in smoking behavior, cognitive dissonance, and motivation to quit: 1) Nicotine Dependence, 2) Past and Current Tobacco Use, 3) Motivation to Quit, 4) Quit Attempts, and 5) Cognitive Dissonance. Nicotine dependence will be measured at baseline and at each follow-up assessment using the Fagerström Test for Nicotine Dependence⁵⁸ and items that assess withdrawal experiences. Past and current tobacco use will be assessed at each time point, including type, frequency, and duration of use. Motivation to quit will be assessed at baseline by asking participants if they want to quit within the next 30 days and at follow-up assessments in terms of stages of change.⁵⁹ We will also use an adaptation of the Contemplation Ladder⁶⁰ that we have used extensively in our prior research^{40,61} and have found in predicting tobacco cessation.^{61,62} Quit attempts will be measured by the number of intentional quit attempts that last at least 24 hours, duration of quitting, and use of pharmacological adjuncts at each time point. Cognitive dissonance will be measured using the Dissonance Thermometer.^{63,64} Prior research⁶³ has shown that the 3- item discomfort factor of the Dissonance Thermometer represents the affective expression of cognitive dissonance.

D.5.3. Statistical Design and Power Overview.

This project will test the *promise* of efficacy of the CDI mobile app with a pre-training, post-training, and 3- month follow-up non-experimental design with 60 adult daily smokers. We hypothesize that after use of the CDI mobile app participants will show increases in quit attempts and number of non-smoking days, and improvement in smoking attitudes and behaviors. We will use random effects growth models to test change in normally distributed outcomes and the Wilcoxon signed-rank test for non-normally distributed outcomes. We also propose ancillary analysis (e.g., dose-response) to bolster our confidence in the non-experimental design. Details of our analytic approach, approach to missing data, power analysis (power >.80 to detect medium effects ($d=.39$) for pre-post change), and feasibility benchmarks are provided in Statistical Design and Power in the Human Subjects.

Reference List

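### Aim 3 treats significant pre-post change as determining efficacy, but the study has no comparator and D.5.3 claims only to test the promise of efficacy

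*Combined protocol and SAP*

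**What the plan says.** Aim 3 in A. Specific Aims sets the rule: "Significant changes in quit attempts, number of days without smoking (smokefree days) and changes in smoking attitudes and behavior will be used to determine". The sentence ends by naming what these changes are to settle: "the efficacy of the Phase I program and evidence for proceeding to Phase II development and evaluation". Efficacy and the case for Phase II are listed there as two separate conclusions.

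D.5.3 (Statistical Design and Power Overview) makes a smaller claim. The project will "test the *promise* of efficacy of the CDI mobile app", and the study is described as a "non-experimental design with 60 adult daily smokers". Its power statement is "power >.80 to detect medium effects ($d=.39$) for pre-post change". It plans random effects growth models for normally distributed outcomes and "the Wilcoxon signed-rank test for non-normally distributed outcomes". It adds ancillary analyses, with dose-response as the example, "to bolster our confidence in the non-experimental design".

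D.4.2 describes a "pilot test of the CDI mobile app with 30 male and 30 female adult smokers". That split is by sex, not by treatment. The entry criteria in D.4.2.a include daily smoking and a stated wish to quit. The supplied text mentions no control arm, randomization, external comparator or historical rate.

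**The concern.** The two sections promise different things from the same data. A single-group comparison of before with after tests whether the mean change differs from zero. It does not test whether the app caused the change. The participants are daily smokers who want to quit and have just enrolled in a cessation study, so more quit attempts and smokefree days are plausible without any effect of the app. D.5.2 also records use of pharmacological aids at each time point, which is another possible source of quitting.

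Dose-response does not supply the missing comparison. Dose here is logged use and modules completed (D.5.2). A more motivated smoker may both use the app more and quit more, so a positive gradient could appear with no app effect.

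If Aim 3 were followed as written, background change would be reported as efficacy and would enter the Phase II decision under that name.

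**Working it through.** **Step 1: compare the claims.**

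| Item | Aim 3 | D.5.3 |
|---|---|---|
| Conclusion drawn | Efficacy, plus evidence for Phase II | Promise of efficacy |
| Basis | Significant change in the listed outcomes | Pre, post and 3-month change in one group |
| Limitation acknowledged | None in the aim | Called non-experimental; ancillary analyses added for that reason |

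The design is the same in both places, so only one of the two conclusions can fit it. With no comparator, it is the weaker one.

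**Step 2: reproduce the plan's own figure.** Inputs are n=60 and d=.39 (D.5.3) and 10-25% non-completion (D.5.1), which leaves 60 × 0.90 = 54 to 60 × 0.75 = 45. Two assumptions are needed because the supplied text does not settle them: a two-sided 5% test, and d taken as mean change divided by the SD of change.

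For a paired t-test, the noncentrality is d × √n and power comes from the noncentral t distribution with n − 1 degrees of freedom.

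- n=60: 0.39 × √60 = 3.02, power 0.844 (normal approximation Φ(3.02 − 1.96) = 0.856).
- n=54: 0.39 × √54 = 2.87, power 0.803. The smallest effect detectable at 80% power is d=0.388, in line with the stated .39.
- n=45: 0.39 × √45 = 2.62, power 0.725.

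The stated power above .80 reproduces at n=60 and at n=54.

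**Step 3: ask what that power refers to.** The calculation uses only the size of the change and not its cause. If a change of size d is wholly background and the app does nothing, the chance of a significant result is the same number.

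| Background change d (assumed) | n=60 | n=45 |
|---|---|---|
| .2 | 33% | 26% |
| .3 | 63% | 50% |
| .39 | 84% | 73% |

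The background values are assumptions; the documents give none. Each entry is for one test on one outcome. The calculation uses a paired t-test on n complete pairs, whereas the plan specifies growth models and an intent-to-treat analysis including everyone, so the table is illustrative and does not predict the trial's results. It is not extended to smokefree days, because the supplied text gives neither a recall window nor a baseline distribution for them.

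**The case against.** The strongest reply is that the statistical section already has this right. D.5.3 italicizes the word promise, calls the design non-experimental, confines power to pre-post change and adds analyses because of the design. Section A also describes the work as testing feasibility, and Aim 3 itself points to further evaluation in Phase II. On this view only a verb phrase in an aims paragraph is at fault. Much of that stands: the tests, sample size and power are sound for what D.5.3 claims, and a Phase I pilot need not have a control group. But Aim 3 is where the plan says how significance will be used, and as worded it reaches a conclusion the design cannot give.

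Three stronger readings are tempting and are not supported.

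- A reader might infer that the plan nowhere limits the meaning of a significant change. That cannot be shown. D.5.3 refers to the Human Subjects section for analytic detail and feasibility benchmarks, and that section was not supplied. It could contain such a limit, although it could not add a comparator to a design called non-experimental.
- A reader might link Aim 3 to B.5, which speaks of marketing an efficacious product. B.5 concerns the proposed app, planned as nine modules (D.4.a), whereas this pilot tests three. Nothing ties the word in B.5 to these tests.
- A reader might cite the voluntariness principle in B.2 as proof that dose is self-chosen. That passage is theory about dissonance induction, and Aim 3 intends all participants to complete the three modules. Self-selected use is a reasonable inference about logged app use, not a stated fact.

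**Conclusion.** Wrong as written. Aim 3 states a rule under which uncontrolled change from baseline determines efficacy, in conflict with D.5.3 and beyond what a single-group design can show. This rests on the documents' wording and on the absence of a comparator, not on any computed value.

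The size of any misattribution is unknown because no background change is given. The 33%, 63% and 84% figures at n=60 rest on the assumed background d, the two-sided 5% level and the paired t-test. A reader might take the 84% as the chance of a false Aim 3 conclusion. It is not: Aim 3 lists several outcomes and does not say that one significant result suffices. Nor is the power statement at fault. It is a correct statement about change against zero.

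**What to change.** 1. In Aim 3, replace the claim to determine the program's efficacy with: *assess the promise of efficacy of the Phase I program*.
2. In Aim 3 and D.5.3, add: *Because there is no control group, a significant change from baseline will be interpreted as preliminary evidence supporting further controlled evaluation, not as a demonstration of efficacy; dose-response results will be interpreted as associations.*
3. Reconcile Aim 3's basis for proceeding to Phase II with the feasibility benchmarks that D.5.3 places in the Human Subjects section, so that one stated set of criteria governs the decision.

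These are wording changes. They need no additional participants, visits, measures or analyses. The downside is a weaker efficacy claim from Phase I.

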D.4.2.a. Participants. Details regarding sample characteristics, eligibility criteria, recruitment and retention are described in the Human Subjects. Briefly, participants will include both male and female adult smokers recruited from the United States. We have a long history of successful recruitment of smokers, and have

extensive experience utilizing recruitment efforts to enroll smokers and tobacco users in mobile app-based intervention programs. Inclusion criteria will be as follows: 1) age 18 or older, 2) self-reported daily smoking, 3) having a valid home mailing address, 4) English-speaking, 5) access to a smartphone with video capability for the duration of the project, 6) not currently enrolled in or participating in any tobacco cessation programs, and 7) expressed desire to quit smoking.

D.5. Data Collection Procedures

D.5.1. Overview and timeline for the pilot study. In the proposed evaluation study, a total of 60 participants will be recruited and baseline assessed during Year 1. We anticipate that approximately 10-25% of these will fail to complete the study; however, we will employ an intent-to-treat analysis strategy, which will include all participants. We will conduct baseline assessments immediately after enrollment and consent; all measures completed at 1-, and 3-month follow-up assessments will be provided online.

The baseline assessment will primarily measure participant risk factors, as well as past and current cigarette and other tobacco use, readiness to quit, quit attempts and cessation in the past year, and will consist of questionnaires administered using Qualtrics; none of the assessments will be done via the mobile app.

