The 1-month assessment will focus on usability, cognitive dissonance, motivation to quit, and short term outcomes such as making a quit attempt, use of the app (dosage), number of cigarettes smoked, and days abstinent from smoking. For the 3-month assessment, the focus will be on cessation outcomes, including both point prevalence (i.e., no smoking in the past 7 days; no smoking in the past 30 days) and sustained abstinence, which is defined as sustained abstinence between the 1- month and 3- month assessment. We will also assess quit attempts at each assessment. Non-responders to the request to complete a follow up assessment will be sent email and text messages to encourage completion of the assessment. We will continue to prompt completion for 14 days following the initial request for the one month assessment and there will be a 30 day window for completion of the 3-month assessment.

D.5.2. Pilot Study Measures. Program navigation and usability will be assessed during usability testing and for the evaluation participants over the one month of use, and will include reports of: 1) ease of use, 2) perceived benefits of using the app, and 3) suggestions for product development modifications. Participants will also provide ratings on product satisfaction and usability on a 7-point Likert Scale. Qualitative data gathered from the focus groups will be recorded and evaluated with the goal of identifying challenges to using the app, product satisfaction, and suggested modifications. This information will then be used to guide adaptations in a Phase II SBIR application. In addition to qualitative data, login tracking information from the app will be used to assess each participant's: 1) frequency and duration of app use, 2) number of modules completed, and 3) type and frequency of substance use. These data will be used to evaluate treatment engagement and adherence, as well as pre- and post- changes in tobacco use.

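### Baseline quit attempts appear to cover a year and follow-up counts have no stated look-back, so the pre-post change may be biased towards a fall or diluted

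*Combined protocol and SAP*

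**What the plan says.** Section D.5.1 lists "readiness to quit, quit attempts and cessation in the past year" among the baseline measures. On follow-up, the same section says "We will also assess quit attempts at each assessment" and gives, for month 1, "short term outcomes such as making a quit attempt". Neither statement carries a recall period. The abstinence outcomes in that section do have one: "no smoking in the past 7 days; no smoking in the past 30 days". Section D.5.2 defines the measure as a count of intentional attempts lasting 24 hours or more, taken at every time point, again with no window.

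The count is then used as a change score. Section D.4.2 says that "quit attempts, and number of days without smoking (smokefree days), will be examined pre- and post-intervention". Section D.5.3 predicts an increase in attempts and assigns non-normal outcomes to the Wilcoxon signed-rank test. Aim 3 opens its list of evidence for efficacy and for Phase II with "Significant changes in quit attempts, number of days without smoking (smokefree days".

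Two response rules in D.5.1 lengthen the follow-up period for late responders. For month 1: "We will continue to prompt completion for 14 days following the initial request for the one month assessment". For month 3: "there will be a 30 day window for completion of the 3-month assessment".

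Sections D.5.2 and D.5.3 refer to the Human Subjects section for the full measures and analytic detail. That section is not among the documents available.

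**The concern.** A count of events depends on how long the respondent is asked to look back. If the baseline item covers 12 months, neither obvious follow-up item gives a like-for-like comparison at 1 or 3 months. A count since enrolment covers far less time than baseline, so its raw change is pulled downwards. A repeated past-year item covers equal time, but most of that time precedes the app. Only a shorter window, the same at both time points, isolates the period of app use.

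The first case works against the study's own hypothesis: an app that raises quit attempts could appear to reduce them. The choice also cannot be repaired later, because a past-year total cannot be split into recent months once collected.

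**Working it through.** **The plan's own figure.** The documents give no figure for quit-attempt windows. The nearest is D.5.3's power above 0.80 for d = 0.39 with 60 participants. Assuming a two-sided 5% test, Φ(0.39 × √60 − 1.96) = Φ(1.06) = 0.856, or 0.844 by the noncentral t. It reproduces, but does not bear on this point.

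**Inputs from the plan.** Baseline window 12 months (natural reading of D.5.1). Follow-up at 1 and 3 months, or about 1.5 and 4 months at the end of the 14-day and 30-day response periods. n = 60. Signed-rank test (D.5.3).

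**Reading (i): follow-up counts run from enrolment.** Expected follow-up count ÷ baseline count = RR × w / 12, where w is the follow-up window in months and RR is the true attempt rate after enrolment divided by the rate before.
- RR = 1: 1/12 = 8.3% at month 1 and 3/12 = 25% at month 3, apparent falls of 92% and 75%.
- Break-even RR = 12/w: 12/1 = 12 and 12/3 = 4; for the latest responders 12/1.5 = 8 and 12/4 = 3.

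These follow from window length alone.

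**Reading (ii): the past-year item is repeated.** The ratio is [(12 − w) + RR × w] / 12. With RR = 3:
- Month 1: (11 + 3)/12 = 1.17, or +17%.
- Month 3: (9 + 9)/12 = 1.50, or +50%.

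With RR = 1 the ratio is 1, so there is no bias towards a fall. The dilution affects the size of the change. With exact recall, the paired difference reduces to the months entering minus the months leaving, so the test keeps the power of a matched window.

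**Reading (iii): one shorter window at every time point.** The unequal-window problem does not arise.

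**Illustration only.** The documents give no attempt rates. Assumptions: 1, 2 or 3 attempts per year on average, gamma-Poisson counts (shape 1), n = 60, two-sided 5% signed-rank test with zero differences dropped, 1,500 simulated trials per cell. Ranges run over the three rates.

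| True rate ratio | Reading (i), month 1 | Reading (i), month 3 | Matched 1-month windows: rise | Matched 3-month windows: rise |
|---|---|---|---|---|
| 2 | fall in 100% | fall in 86–100% | 24–58% | 57–95% |
| 3 | fall in about 100% | fall in 27–69% | 58–97% | 96–100% |
| 5 | fall in 95–100% | rise in 23–55% | not run | not run |

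With no true change, reading (i) gives a significant fall in about 100% of trials at both months. Matched windows reject in 3.5–5.3% in total.

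**Selection at entry.** Section D.4.2.a requires self-reported daily smoking. Someone who recently stopped for 24 hours or more may be less likely to qualify, which would lower recent baseline counts. Suppose screening removes half of those with an attempt in the last month. With no true change, matched windows then give false significant rises in about 6–20% of trials at 30 days and 6–10% at 3 months, against a nominal 2.5%. The strength of this screening is unknown.

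**The case against.** The strongest reply is that the text leans against reading (i). Section D.5.2 gives one definition of quit attempts for every time point. Where a measure changes between baseline and follow-up, as motivation to quit does, D.5.2 says so. That favours the same item throughout, which gives reading (ii) or (iii), and neither is biased towards a fall. No passage says that follow-up counts start at enrolment. The reference to the past year could also attach to cessation only. Both sections are summaries that refer to the Human Subjects section, where recall windows would normally be set. The month 1 outcome may be yes/no, in which case the signed-rank percentages for month 1 do not apply.

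This limits the point but does not remove it. A reader might infer that the plan compares a year with a month and will therefore report a spurious fall. The documents do not support that inference: it needs one of three open readings, and not the one the wording favours. What stands is narrower. With a past-year baseline, a same-item follow-up is diluted and a since-enrolment follow-up is biased downwards. If the past-year phrase covers cessation only, the available text states no window for quit attempts at any time point, and the same clarification is needed.

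It is also fair to say that reading (i) errs against the app and so cannot create false efficacy, and that matched recent windows carry the selection problem shown above. A past-year window is less exposed to it.

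**Conclusion.** The point holds in conditional form. On the natural reading of D.5.1 the baseline quit-attempt count covers 12 months, and the available text does not make the follow-up counts comparable with it.

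- If they run from enrolment, the attempt rate must rise more than 12-fold at month 1 or 4-fold at month 3 (about 8-fold or 3-fold for the latest responders) before the mean count rises.
- If the past-year item is repeated, the comparison is fair given accurate recall, but the change is diluted by 11 or 9 months before enrolment.
- If one shorter window is used throughout, neither problem arises.

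The break-even and dilution figures need only the window lengths and a steady rate before enrolment. All simulated percentages rest on assumed attempt rates and dispersion. Severity is low to moderate: quit attempts are one of several outcomes informing Phase II, in a pilot that tests only the promise of efficacy. A reader might conclude that this flaw alone could decide Phase II; aim 3 does not support that.

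**What to change.** If the Human Subjects section already sets matched look-backs, state them in D.5.1 and D.5.2; nothing more is needed. Otherwise, before baseline data are collected:

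1. Ask about 24-hour attempts in the past 3 months at baseline and month 3, and make this the main quit-attempt comparison.
2. Ask about the past 30 days at baseline and month 1, as a secondary comparison.
3. Compare only matched windows, with the planned signed-rank test. Do not add the month 1 and month 3 counts, because their windows can overlap.
4. Keep the past-year count as a descriptor or covariate.

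If only a past-year baseline exists, a count model with a log-exposure offset is the fallback. It assumes a steady rate and accurate recall over 12 months. Dividing counts by months and keeping the signed-rank test is not safe at month 1: with no true change it gave false falls in 28–64% of simulated trials.

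The cost is two baseline questions, identical wording at follow-up and a sentence in the protocol. The downsides should be stated:
- The 30-day window has more zeros and less power. With 25% loss (n = 45), power for a tripled rate is 44–90% at 30 days and 89–100% at 3 months, under the same assumptions.
- For late responders, a fixed window misses up to the first 14 days (month 1) or 30 days (month 3) after enrolment.
- Daily smoking at entry may select for few recent attempts and so bias towards a rise, more at 30 days than at 3 months. A rise in the 30-day comparison should be read with caution.

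### D.5.2 measures motivation to quit with one instrument at baseline and another at follow-up, so neither gives the planned pre-post change; the Contemplation Ladder could, but its time points are not stated

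*Combined protocol and SAP*

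**What the plan says.** Two places commit the pilot to a pre-post comparison of motivation. D.4.2 (Stage 2: Product Evaluation) states that "smoking attitudes and behavior, including motivation to quit, quit attempts, and number of days without smoking (smokefree days), will be examined pre- and post-intervention". D.5.2 (Pilot Study Measures) introduces its list of five measures, of which motivation to quit is the third, by saying that "the following will be used to examine pre- and post- changes in smoking behavior, cognitive dissonance, and motivation to quit".

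D.5.2 then sets out how motivation is measured: at "baseline by asking participants if they want to quit within the next 30 days and at follow-up assessments in terms of stages of change". The next sentence adds a third instrument, "We will also use an adaptation of the Contemplation Ladder", with no assessment named for it.

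The list is explicitly a summary: "A full description of measures is included in the Human Subjects". That section is not among the documents supplied.

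For the analysis of change, D.5.3 says: "We will use random effects growth models to test change in normally distributed outcomes and the Wilcoxon signed-rank test for non-normally distributed outcomes".

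**The concern.** A within-person change from before to after the intervention needs the same quantity recorded before and after. D.5.2 states one motivation instrument for the pre assessment and a different one for the post assessments. A participant's answer about wanting to quit within 30 days and a later stage of change are not on a common scale, so they cannot be subtracted, ranked as a signed difference, or entered as repeated values of one outcome in a growth model.

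What is at stake is modest but real. Aim 3 (section A) counts changes in smoking attitudes and behavior, alongside quit attempts and smokefree days, as evidence for going on to Phase II, and D.4.2 places motivation within that group. A baseline value that was never collected cannot be recovered once the participant has used the app.

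**Working it through.** **The plan's own figure.** The only design figure nearby is the power in D.5.3: above .80 for d = .39 in pre-post change. Alpha is not stated, so I assume two-sided 0.05 and a paired t-test with n − 1 degrees of freedom and noncentrality d√n.

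- n = 60: 0.39 × √60 = 3.021, power 0.844.
- n = 54 (10% loss): 0.39 × √54 = 2.866, power 0.803.
- n = 45 (25% loss): power 0.725.

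The stated figure therefore reproduces with 60 enrolled and 10% loss. It does not depend on which motivation instrument is used, and this point does not dispute it.

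**Instrument against time point.** Assessments are at baseline, 1 month and 3 months (D.5.1). Setting out what D.5.2 states:

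| Motivation instrument | Baseline | Follow-up | Baseline-to-follow-up pair |
|---|---|---|---|
| 30-day question | yes | not scheduled | no |
| Stages of change | not scheduled | yes | no |
| Adapted Contemplation Ladder | not stated | not stated | cannot be determined |

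Of the 2 instruments with stated time points, 0 have both a baseline and a follow-up value. D.5.2 refers to follow-up assessments in the plural, so stages of change can be read as given at both month 1 and month 3. It can then show movement between those two points, but that interval starts after the intervention has been used and is not the pre-post change.

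**Comparison with neighbouring measures.** The same paragraph puts nicotine dependence at baseline and every follow-up on one named test, and puts tobacco use and quit attempts at each time point. For motivation it states a split schedule, which is more than an omission. By contrast, the Ladder and the Dissonance Thermometer are simply left without time points there.

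**Other references to motivation.** D.5.1 says the baseline covers readiness to quit and the 1-month assessment covers motivation to quit. Neither statement names an instrument. Both fit a Ladder given before and after, but do not establish it.

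**What a baseline stage item would add.** D.5.1 expects 10-25% of 60 not to complete. Assuming that non-completers are those without a 3-month response:

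- 25% loss: 60 × 0.75 = 45 pairs.
- 10% loss: 60 × 0.90 = 54 pairs.

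Same-scale stage pairs from baseline to month 3 would rise from 0 to about 45 to 54. Month 1 may have more.

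**The case against.** The best case for the plan is that the Ladder already does this job. It is listed under the pre-post lead-in, it directly follows the motivation sentence, and D.5.1 has readiness to quit at baseline and motivation at 1 month. D.5.2 is a brief summary, and it also gives no time points for the Dissonance Thermometer, so silence about timing is weak evidence that an assessment is missing. All of this stands. A reader might infer that the pilot has no way to measure change in motivation. The documents do not support that: the Human Subjects section may well schedule the Ladder before and after.

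A reader might also infer that the stage item can show no change at all. That too goes too far, since movement from month 1 to month 3 remains available.

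It can further be said that the response format of the 30-day question and the content of the staging items are not given. If the follow-up staging repeated the same 30-day question, a common yes/no comparison could be derived. The documents do not say that it does.

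Finally, motivation is not named in Aim 3's criteria or in the D.5.3 hypothesis, and nothing says that the stage item was meant as a change score. This limits the weight of the point. It does not remove the mismatch between the split schedule that D.5.2 states and the pre-post use that D.4.2 and D.5.2 plan.

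**Conclusion.** The point holds as a limited one. Followed as written, the D.5.2 schedule gives neither the 30-day question nor stages of change a baseline-to-follow-up pair (0 of 2). Whether the planned motivation comparison exists therefore rests on the Ladder, whose time points the supplied text does not give. If the Ladder is collected before and after, the comparison is available and what remains is to say so and name it as the outcome. If it is not, no stated instrument provides pre-post change in motivation.

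The conclusion rests on reading D.5.2 literally and on not having the Human Subjects section. The figure of 45 to 54 pairs also assumes that non-completion means no 3-month response. The effect is confined to one secondary construct in an uncontrolled 60-person pilot. It would be wrong to infer that the Phase II decision or the sample size is undermined, because quit attempts, smokefree days and the power figure do not depend on this.

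**What to change.** Ask the stage-of-change item with identical wording at baseline, month 1 and month 3. Confirm that the Ladder is given at the same three assessments, or add it there if it is not. Name one of the two in D.5.2 as the motivation change outcome; the Ladder is the natural choice if it is already repeated. Keep the 30-day question as a baseline descriptor. Repeating that question would be a less attractive repair, because eligibility already requires an "expressed desire to quit smoking" (D.4.2.a), which may leave little room for improvement. If the Human Subjects section already sets such a schedule, bring D.5.2 into line with it.

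The cost is one stage item, plus the Ladder if it is not already there, in a baseline assessment that "will consist of questionnaires administered using Qualtrics", and one or two sentences in D.5.2. The downside is about a minute of extra baseline questionnaire time.
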